Training of the NP ([name]) will be supervised by [name], and include a 3-day introductory intensive workshop introducing the theory, principles, and skills of MI and related motivation-enhancing, behavior change approaches; and a 3-day advanced training workshop. Learning activities will include demonstrations, video examples, “real-plays”, case studies, and small group exercises. Pilot MI+GOW sessions completed by [name] will be evaluated using global ratings from the MI Treatment Integrity coding system 4.0. Prior to counseling study participants, ratings ≥ 3 on all global scores (cultivating change talk, softening sustain talk, partnership, and empathy) of 2 consecutive pilot participants will be required. Ongoing supervision of MI skills will include monthly reviews of recorded interventions (after MI treatment integrity coding) and meetings with [name] to optimize treatment fidelity and minimize drift.

The Principal Investigator (PI), [name], will train the NP ([name]) on the components of the enhanced usual care calls including topics of: 1) standardized instructions on taking opioid medications after surgery, 2) safe opioid use, 3) avoiding medication mistakes, 4) local mental health resources (including a suicide prevention hotline), 5) alternative methods for pain management after orthopedic surgery, 6) understanding complementary and alternative medicine, and 7) prescription drug abuse.

Principal Investigator

The Principal Investigator, [name], will speak directly with all participating surgeons and preoperative clinic staff to inform them of the purpose of the research and the process for recruitment and patient referrals. Referring physicians will be informed of the study design such that they are aware of what intervention their patients may be receiving. A Q&A form will also be provided to the patient's physician(s) for informational purposes.

MAP-Pain Standard Operating Procedures

Recruitment

Recruitment may take place via one of following methods:

Clinical staff referral

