Randomization table was pre-generated using SAS. Randomization occurs using blocked, stratified randomization by operation. Randomization table was pre-generated onto spreadsheets, with rows hidden (in Excel). Each randomized patient will receive the next available row (unhidden by the coordinator at 14 days post-surgery for randomization as needed).

The PI will be blind to the patient's randomization status until completion of analyses. Due to the limitations of REDCap's randomization module, the research coordinator cannot be blinded to the randomization status of the participant.

Enhanced Usual Care (EUC)

Participants will receive phone calls matching the duration and frequency of MI+GOW calls. [name], NP will contact participants via phone to review one topic per call in this sequence: 1) standardized instructions on taking opioid medications after surgery, 2) avoiding medication mistakes, 3) alternative methods for pain management after orthopedic surgery, 4) understanding complementary and alternative medicine, 5) safe opioid use, 6) local mental health resources (including a suicide prevention hotline), 7) prescription drug abuse. She will briefly review patient education brochures in a didactic style without a tailored discussion. She will remind participants to complete REDCap assessments.

Intervention

The experimental intervention arm is Motivational Interviewing and Guided Opioid Weaning (MI+GOW). A pain medicine nurse practitioner ([name], NP) will administer MI+GOW. See table below for MI Components. The GOW protocol will be a 25% total daily opioid dose reduction every 7 days with opioid discontinuation 7 days after reaching 1 opioid pill per day. During phone sessions, patients will be monitored for worsening pain and opioid withdrawal through administration of the NRS and SOWS with the protocol specified in the "Guided Opioid Weaning" table below. Participants will be reminded that they can always use less opioids than recommended. Non-adherence is opioid use greater than previously recommended via the last phone call. During the randomization call, the first MI appointment should be scheduled by referring to [name]'s schedule.

Table MI Components

Principles	Strategies	Information Recorded by Interventionist	Information and Advice Offered in an MI-consistent manner (Elicit patient's knowledge, Provide advice, Elicit feedback)
------------	------------	---	---

MAP-Pain Standard Operating Procedures

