The first session will be scheduled by the research coordinator; subsequent appointments will be made directly between the NP's and the patient. The first session must be scheduled between 14 and 21 days after the participant's date of surgery. After the initial call, NP's will be responsible for tracking and competing intervention calls.

Intervention Protocol

Participants randomized to MI+GOW will receive the intervention from a single provider ([name]). Of note, participants will have all opioids and additional pain medications prescribed by their surgeon during the study. [name] will only be providing advice regarding participants' opioid medications. Content of the MI call is detailed in the Intervention section above. Treatment engagement is defined as participation in >50% of phone sessions. Treatment initiation is defined as participation in at least 1 phone session.

Longitudinal Follow-up

Scheduling Follow-Up Assessments

Electronic surveys will be sent out automatically based on confirmed dates of surgery. Distribution of online assessments will occur via the REDCap survey invitations calendar defined in the Longitudinal Observation Project, beginning seven days after the date of surgery. A patient's official date of surgery will be entered into the "Pre-Surgery Call" instrument in REDCap during the Pre-Surgery call, and confirmed during the Post-Surgery call. The study team member may verify the date of surgery and time of discharge in EPIC and record it on the "Post-Surgery Call" instrument.

Medical Chart Review

Research team member will review the patient's medical record for information required on the case report form.

Compliance Monitoring

Participant compliance with follow-up assessments will be assessed weekly through an automated reporting dashboard. Patients failing to complete two consecutive follow-up assessments be contacted

MAP-Pain Standard Operating Procedures

by the research coordinator, to encourage continued participation. The coordinator may offer to limit the participant's follow-up to monthly surveys, to maintain follow-up data collection for the participant.

Survey Frequency Reduction

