 - a. PROMIS Bank v1.0- Depression
 - b. PROMIS Bank v1.0- Anxiety
 - c. PROMIS Bank v1.0- Sleep Disturbance
 - d. PROMIS Bank v2.0- Physical Function

Monthly Assessments from 6 to 12 months

From 6 to 12 months, online assessments alternate to reduce participant burden. These assessments can be grouped in to the following categories

Regular Monthly Assessments

Administered via online survey monthly. Assessments Include:

1. Common Opioid Misuse Measure (COMM)
2. PROMIS Measures
 - a. PROMIS Bank v1.0- Sleep Disturbance
 - b. PROMIS Bank v2.0- Physical Function

Alternating Monthly Assessments

These assessments alternate each month, the help reduce participant burden. Assessments Include:

1. Patient Health Questionnaire-9 (PHQ-9): Assessed on Weeks 24, 32, 40, and 48
2. PROMIS Measures: Assessed on Weeks 28, 36, 44, and 52.
 - a. PROMIS Bank v1.0- Depression
 - b. PROMIS Bank v1.0- Anxiety

Irregular Assessments

The following assessments are to be completed via online assessment at time points in addition to Weekly/Monthly Assessments, or have schedules that are best described more specifically.

1. Self-Efficacy for Appropriate Medication Use Scale (SEAMS): Administered to intervention participants on Week 1 only
2. Motivation Interviewing Rulers (MI-Rulers): Administered to intervention participants on Weeks 2, 4, 7, and 12 only

Censoring

Participants may be withdrawn for the following reasons:

- Additional surgery
- Postoperative complication
- Death

MAP-Pain Standard Operating Procedures

- Patients expressing concerns regarding pain management will be offered study withdrawal and referral to a pain medicine specialist

Withdrawn participants will be removed from all future data collection.

Patient Withdrawn or Study Completion

If a patient is withdrawn from the study, or lost to follow-up, the study coordinator will document the events by filling out the “Study Stop Point” instrument electronically in REDCap.

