Patient Adherence

Non-adherence is considered greater than recommended opioid use that is still within the range of the patient's prescription.

Patient Retention

Patient retention is at its highest rate when participants feel like they are aware of what is occurring in the study, when they have their needs met, and when they are greeted with optimistic and attentive staff.

To keep participants engaged:

- Research staff must ensure that participants know exactly what the study goals are and how the study staff are working to meet these goals.
- Participants should be completely aware of what is required for effective, active participation. The level of time commitment must be made clear at the beginning in order to avoid future dissatisfaction.
- Participants should know that we greatly appreciate their efforts, especially since they are volunteering their time. It must be made clear how important their contribution is to this science.
- Participants must be told that they can withdraw from the study at any time even though we would be sad to let them go. They must be made aware of the effort it takes on all fronts in designing this study and collecting data, so they should try their best to remain in the study.
- Research staff must ensure that all other staff know what to communicate to participants, especially in times of dissatisfaction.

To retain participants who are dissatisfied with the study:

- If the issue comes from participants feeling overwhelmed by assessments, research staff must make an effort to reduce assessments. (See *Survey Frequency Reduction* above)

MAP-Pain Standard Operating Procedures

Trial Safety

Potential Risks & Response to Risks

Risk of Telephone Contact

The primary risk of telephone and online contact involves breach of confidentiality. All research personnel are trained in confidentiality procedures and adequate protections will be in place to minimize this risk. All research personnel must be HIPAA trained. Personnel enrolling participants must complete CITI training.

Risks of Intervention

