In addition to risks of confidentiality, there are few other risks involved in enrollment into the intervention. Those who are randomized into MI+GOW may be exposed to greater risk. These risks, however, are only relevant if a participant follows the recommendations. Because [name] is not a part of a participant's regular care team, the participant has the freedom to choose which recommendations to follow, with no obligation to follow any at all. [name]'s role is to recommend courses of action that meet the participant's needs, to the extent that it does not do additional medical harm.

Despite these rules, the following are risks that may be associated with participating in MI.

The physical and psychological risks to subjects are the effects opioid withdrawal including tachycardia, diaphoresis, restlessness, rhinorrhea, bone or joint aches, gastrointestinal upset, tremor, irritability, anxiety, and piloerection. Also, patients may experience increased pain if opioids are tapered prematurely. The seriousness of these side effects is moderate, as withdrawal symptoms and pain will be monitored during the intervention. Protocols are in place to hold the tapering schedule with the development of moderate opioid withdrawal and to increase the opioid dose with the development of severe pain. This type of opioid withdrawal is not fatal (as opposed to iatrogenic opioid withdrawal precipitated by opioid antagonists that could lead to mortality). Patients will be encouraged to contact the nurse practitioner ([name]) at any time regarding the development of any adverse effects. Patients will be able to reach the PI ([name]) or an alternate qualified member of the research team 24 hours a day. Also, participants reporting dramatically increased pain potentially related to other medical causes-e.g. infection, dislocation, thromboembolic disease, new neurologic deficits, will be referred to their nearest emergency department, and their PCP or surgeon will be contacted at the discretion of [name] or [name].

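### The weaning table advises a 25% dose increase whenever NRS exceeds 7, and no stated rule keeps the advised dose within the surgeon's current prescription

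*Protocol*

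**What the plan says.** All of the relevant text is in the Protocol; the SAP does not touch the point.

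- **The dosing rule.** The Guided Opioid Weaning Protocol table has four rows, formed by mean SOWS (above 2, or 2 and below) and NRS (above 7, or 7 and below). Both rows with NRS above 7 give a 25% increase in total daily dose. With NRS at 7 or below, the dose is held if SOWS is above 2 and cut by 25% otherwise.
- **The increase is deliberate.** Risks of Intervention says that protocols are in place "to increase the opioid dose with the development of severe pain".
- **Who prescribes and who advises.** Intervention Protocol states that "participants will have all opioids and additional pain medications prescribed by their surgeon during the study" and limits the nurse practitioner to advice. Table MI Components lists advice that follows the weaning table under the column "Information and Advice Offered in an MI-consistent manner".
- **Where the prescription is mentioned.** Table MI Components has the nurse practitioner tell patients what the surgeon currently prescribes. Patient Adherence describes non-adherence as "greater than recommended opioid use that is still within the range of the" prescription.
- **The nearest safeguards.** Under Risks of Intervention, recommendations serve the participant's needs "to the extent that it does not do additional medical harm". For dramatically increased pain that may have another medical cause, patients go to the emergency department and "their PCP or surgeon will be contacted at the discretion of" study staff. Under Censoring, patients who voice concerns about pain management "will be offered study withdrawal and referral to a pain medicine specialist". Under Education and Training, the principal investigator "will speak directly with all participating surgeons and preoperative clinic staff to inform them of the purpose of the research".

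**The concern.** The weaning table is a dosing algorithm run by someone who does not write the prescription. Its upward step depends only on the pain score. It does not ask how much of the prescribed dose the patient already takes, and it does not stop at the prescribed dose. A patient close to that dose who reports severe pain could therefore be advised by trial staff to take more opioid than the surgeon has authorised.

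The stake is safety and clear clinical responsibility in the MI+GOW arm. A limit of this kind is better written beside the rule than left to be inferred.

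**Working it through.** The plan gives no figure to reproduce here. The check has two parts: reading the rule against the surrounding text, and finding when its output passes the prescription.

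**1. The table, cell by cell**

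| | NRS 7 or below | NRS above 7 |
|---|---|---|
| Mean SOWS 2 or below | 25% decrease | 25% increase |
| Mean SOWS above 2 | hold | 25% increase |

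Both cells with NRS above 7 advise an increase, so SOWS has no bearing once pain passes that threshold.

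**2. Does any text cap the advised dose?**

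- Patient Adherence takes it for granted that the recommended dose lies within the prescription. It classifies what the patient does; it does not bind the adviser.
- Table MI Components puts the prescription in front of both parties during the call, but states no limit.
- The no-harm wording in Risks of Intervention is general and does not mention the prescription.
- Surgeon contact in the same section is discretionary and tied to pain with a possible other cause. It is not a condition for advising an increase.
- The withdrawal and referral offer under Censoring depends on the patient raising a concern.
- The briefing of surgeons is about the study's purpose and process. As described, it sets no dose limit.
- The relapse-prevention row of Table MI Components mentions encouraging contact with the surgical team, as an example of building self-efficacy.
- The Intervention section's reminder on dose is that patients may take less than advised.

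None of these is a cap, a maximum number of increases, or a requirement to consult the surgeon first. This covers the text supplied; the physician Q&A form and the Appendix are not shown.

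**3. When does the advice exceed the prescription?**

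Let s be the daily dose now taken, as a share of the most the current prescription allows. After one call with NRS above 7 and the prescription unchanged:

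advised share = 1.25 × s

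This exceeds 1 when s > 1/1.25 = 0.80. The documents do not give s, so the values below are assumptions that show the range.

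| Share taken at the call (assumed) | Advised share of prescription |
|---|---|
| 60% | 1.25 × 0.60 = 75% |
| 80% | 1.25 × 0.80 = 100% |
| 90% | 1.25 × 0.90 = 112.5% |
| 100% | 1.25 × 1.00 = 125% |

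**4. The effect of the taper**

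A patient who began at the full prescription, took one 25% step down and then reported NRS above 7 would be advised 0.75 × 1.25 = 0.9375, or 93.75%. That is still within the prescription. The overshoot therefore concerns patients above 80% at the time of the call, mainly those who have not yet reduced or who have had repeated increases.

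**The case against.** The strongest reply is that within-prescription advice is the natural reading. Only the surgeon can supply opioids. The adviser is a pain medicine nurse practitioner who tells the patient what is prescribed. The Patient Adherence wording assumes advice inside the prescription, and the no-harm principle would let the nurse practitioner hold at the prescribed dose. Patients need not follow the advice, and an internal panel reviews safety every 3 months. On this view the plan leaves an assumption unstated; it does not lack the safety concept. Much of this stands and is why the point is graded low. It does not supply the rule: the table as written directs an increase, and nothing shown says where to stop.

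The size is also open to challenge, because every share in the working is assumed and the frequency of NRS above 7 is unknown. That stands too. The 80% threshold follows from the table alone, but the number of patients affected cannot be derived.

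Two stronger readings are tempting, and the documents do not support them.

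- A reader might infer that non-adherence becomes impossible to record once the advice reaches the prescription, since no dose is then both above the advice and within the prescription. The Intervention section has a second definition, use above what was advised at the last call, which has no prescription bound. Under the Patient Adherence wording, a cap would change nothing: for s of 0.80 or more, the advice is at least the full prescription without the cap and exactly the full prescription with it, so the interval is empty for the same patients.
- A reader might infer that the Protocol itself acknowledges this hazard when it says the MI+GOW arm may carry more risk. The risks it then lists are withdrawal and pain from tapering too early. The dose increase is offered as the remedy for the latter.

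**Conclusion.** The point holds as a low-severity safety clarification. With the prescription unchanged and the table followed literally, a single call with NRS above 7 leads to advice above the surgeon's prescription for any patient taking more than 80% of it, up to 125% for a patient taking all of it. Patients at or below 80% stay within it.

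The conclusion rests on three assumptions: the nurse practitioner applies the table without holding back on clinical judgement, the surgeon has not changed the prescription, and the material not shown contains no cap.

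A reader might go further and compound the increases over all seven calls, or infer bias in time to opioid cessation or in the misuse outcome. The first would need NRS above 7 at every call, with each increase taken and built on the last, and nothing in the documents suggests that course. For the second, the documents give neither how often the situation arises nor how often patients act on the advice. No effect on any endpoint is claimed.

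**What to change.** Add two sentences under the Guided Opioid Weaning Protocol table:

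> The advised total daily opioid dose may not exceed the daily dose currently prescribed by the surgeon. If the table output would exceed it, the nurse practitioner advises no more than the prescribed dose and refers the patient to the surgeon; a higher dose is advised only after the surgeon has changed the prescription.

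Increases within the prescription remain available, and larger ones go to the prescriber. The change needs no new visits, calls or analyses, and the current prescription is already part of the call content in Table MI Components. The cost is that a patient in severe pain at the prescribed limit waits for the surgeon's decision. The 24-hour contact with the principal investigator or another qualified team member, described under Risks of Intervention, remains available meanwhile.

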To reduce instances of participants lost to follow-up or withdrawing, the coordinator can reduce the frequency of participant surveys from weekly to monthly. To complete this, the coordinator will check the "Monthly Surveys Only" checkbox in the "Coordinator Controls" instrument of the Longitudinal Observation REDCap project, and save the instrument.

Lost to Follow-up Participants

A participant is considered "Lost to Follow-up" if they have not completed a follow-up assessment for two months, and cannot be reached by the research coordinator. The Research coordinator will attempt to call the participant three times before declaring them lost to follow-up, leaving a voicemail message. If a participant has alternative numbers listed (like a spouse or relative), those numbers should be attempted many times before inactivating the participant.

If the coordinator has determined the participant is lost to follow-up, the coordinator will mark the participant status as "Inactive" in the Coordinator Controls Instrument of Longitudinal Observation REDCap. The coordinator will also input the date of last contact with the participant, and select "Lost to follow-up" as the reason for withdrawal. Participant notes may be used to elaborate on the circumstances of the participant's withdrawal.

Patient Withdrawn or Study Completion

If a patient is withdrawn from the study, the study coordinator will mark the participant status as "Inactive" in the Coordinator Controls Instrument of Longitudinal Observation REDCap and document the date of the last contact and reason for withdrawal. The study coordinator will also input the date of last contact with the participant, and select "Lost to follow-up" as the reason for withdrawal. Participant notes may be used to elaborate on the circumstances of the participant's withdrawal.

Weekly and Monthly Surveys

Weekly Assessments

The following assessments will be completed weekly via online assessment up to 6 months, and then monthly up to 12 months for all participants.

1. Weekly Pain and Opioid Questionnaire (WPOQ, combined into one instrument with BPI)
2. Modified Brief Pain Inventory-II (BPI, combined with WPOQ into one instrument)

Monthly Assessments up to 6 months

The following assessments will be completed monthly via online assessment up to 12 months for all participants.

1. Patient Health Questionnaire-9 (PHQ-9)

MAP-Pain Standard Operating Procedures

2. Common Opioid Misuse Measure (COMM)
3. PROMIS Measures

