An additional 10% of data will be randomly verified by study staff prior to data analysis. Verification will occur via visual inspection. Discrepancies will be noted, original source data checked, and the correct value entered. All verified data will be noted with the reviewer's initials and date. Corrections will be noted with the date, initials, and reason for correction. Consistent errors will prompt a more comprehensive review of the data at the PI's discretion.

MAP-Pain Standard Operating Procedures

Primary Efficacy Outcome-Observation Arm

Time to opioid cessation, defined as the first of 2 consecutive reports of opioid cessation on the modified BPI.

Secondary Efficacy Outcomes-Observation Arm

1. Opioid misuse (This will be defined as a score of 9 or higher on the Current Opioid Misuse Measure).
2. Time to pain cessation (This will be defined as the first of five consecutive days of 0 average pain).
3. Time to recovery (First report of patient indicated "Yes" to having recovered from surgery).

Primary Efficacy Outcome-Intervention Arm

Time to opioid cessation, defined as 1st of 2 consecutive reports of return to baseline opioid dose or lower.

Secondary Efficacy Outcomes-Intervention Arm

1. Opioid misuse (This will be defined as a score of 9 or higher on the Current Opioid Misuse Measure).
2. Time to complete opioid cessation, defined as the first of 2 consecutive reports of opioid cessation on the modified BPI.
3. Time to pain cessation (This will be defined as the first of five consecutive days of 0 average pain).
4. Time to recovery (First report of patient indicated "Yes" to having recovered from surgery).
5. Treatment engagement is defined as participation in >50% of phone sessions.
6. Treatment initiation is defined as participation in at least 1 phone session.

Methods for handling missing data and non-adherence to protocol:

Subjects dropping out will be censored at the last known data point. Competing events such as a second surgery will be reasons for censoring at the time of the competing event. Missing data will not be imputed.

Modifications History

Last Updated 10/15/2020 by [name], CRC.

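### The protocol asks for the reason for withdrawal, then fixes that reason as loss to follow-up, so the coded field cannot separate withdrawals from true losses

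*Protocol*

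**What the plan says.** The protocol has two sections headed Patient Withdrawn or Study Completion. The one under Longitudinal Follow-up has the coordinator set a withdrawn patient to inactive in the Coordinator Controls instrument, then "document the date of the last contact and reason for withdrawal. The study coordinator will also input the date of last contact with the participant". The second of these sentences, which repeats the request for the last-contact date, adds the instruction to "select 'Lost to follow-up' as the reason for withdrawal". A closing sentence makes free text optional: "Participant notes may be used to elaborate on the circumstances of the participant's withdrawal".

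The section just before it, Lost to Follow-up Participants, defines that status. A participant is lost "if they have not completed a follow-up assessment for two months, and cannot be reached by the research coordinator", after three attempted calls.

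The Censoring section opens "Participants may be withdrawn for the following reasons" and lists a further surgery, a complication after surgery and death. It also says that patients with concerns about pain management will be offered withdrawal.

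The other section headed Patient Withdrawn or Study Completion, which follows Censoring, requires a separate Study Stop Point instrument for patients who are withdrawn or lost. It places the inactive status in an instrument called Participant Entry.

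The section on missing data and non-adherence sets two censoring rules: "Subjects dropping out will be censored at the last known data point" and "Competing events such as a second surgery will be reasons for censoring at the time of the competing event". The SAP adds nothing on censoring.

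**The concern.** A patient withdrawn because of a second surgery is not lost to follow-up: the patient has been reached and the cause is known. A coordinator who follows the text as written would nevertheless enter that code, with a last-contact date beside it. The field would then hold one value for every patient who left early and could not show why anyone left.

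Two uses of the record are exposed. The DSM report to NIDA includes retention and disposition of participants, and a disposition table built on this field would show withdrawals for complications or pain concerns as losses. The primary outcome in both arms is a time to event, and the protocol's censoring rule needs two things for a competing event: knowledge that it occurred, and its date. This paragraph secures neither in the coded field.

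**Working it through.** The documents give no design figure to reproduce here, so the check sets the texts side by side.

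1. **Within the paragraph.** One sentence asks for the reason. The next supplies a fixed answer. Both cannot govern, and nothing says which does.

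2. **Against the definition.** Loss to follow-up needs two months without an assessment and failed contact. A patient withdrawn for a further surgery, a complication or a pain concern need not meet either condition. For such a patient the instructed code is false under the protocol's own definition.

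3. **Against the Censoring list.** The reasons there are distinct and would matter to a reader of a disposition table. The instruction merges them all into a category that is not on that list.

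4. **Against the censoring rule.** Dropouts are censored at the last data point and competing events at the event. The paragraph asks only for the date of last contact. The two dates can differ in either direction. If the last contact was a survey before the event, a patient answering every survey would show a gap of up to about a week while surveys are weekly (to 6 months) and up to about a month afterwards, or earlier if that patient was moved to monthly surveys. If staff learn of the event by a later telephone call, last contact falls after it.

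5. **What a wrong date would do.** The planned Kaplan-Meier, log-rank and Cox analyses treat dropouts and competing events alike, as censored. The reason code does not enter the model; only the date can matter. A shifted censoring date changes a risk set only if another patient reaches the endpoint between the two dates, and it changes nothing for a patient who had already reached the endpoint.

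6. **Other records.** Study Stop Point is required for the same patients, but its fields are not described and no text makes it the source for censoring. Participant notes are optional and uncoded. The two withdrawal sections also name different instruments for setting the inactive status.

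7. **Scale.** Study Overview assumes 10% censoring in the intervention arm and 15% attrition in the observational arm: 220 × 0.10 = 22 and 558 × 0.15 = 83.7, about 84. These are planning totals for all causes. True losses among them would be coded correctly, and the documents give no split by reason. Under those assumptions the number miscoded lies anywhere from 0 to these totals.

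**The case against.** The strongest reply is that this is a copying slip with little consequence. The disputed wording closely repeats the lost-to-follow-up section above it, which suggests that it was carried over by mistake (an inference). The same paragraph asks for the true reason, Study Stop Point is a second record, medical charts are reviewed, and the section Trial Stopping Rules says that a participant's own decision to stop will be noted. No text makes the Coordinator Controls field the source of censoring dates.

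Most of this stands, and it rules out several stronger readings that a reader might infer:

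- **That the reasons for withdrawal are lost to the trial.** The documents do not show this. Another required form may hold them.
- **That harms would be hidden from safety review.** SAEs go on their own NIDA form. Adverse events are reported in aggregate to NIDA and the IRB each year and to the DSMB each quarter. The DSM report lists AEs and SAEs apart from disposition. Only the disposition item is exposed, and no text says that it is drawn from this field.
- **That the primary analysis is wrong.** This holds only if the field and its date feed the analysis, which is not stated.
- **That 22 and 84 patients would be miscoded.** Those are total planned censoring and attrition.

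What the reply does not remove is that this is an operating procedure which staff follow, that it instructs a false entry, and that no document says which record governs.

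**Conclusion.** The contradiction is certain, because it is on the page. Followed literally, it makes the Coordinator Controls reason field unable to distinguish withdrawal for surgery, complication, death or pain concerns from true loss to follow-up. The retention and disposition item of the DSM report could be wrong as a result.

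The effect on the time-to-event analysis is conditional. If this field and the last-contact date are used, competing events could be censored at the wrong date. If Study Stop Point or the chart is used, and holds the reason and event date, there is no effect. AE and SAE reporting is not affected. The number of patients concerned cannot be derived from the documents. The point should be corrected, as an internal inconsistency in data handling; it is not a flaw in the trial's design.

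**What to change.** - Replace the sentence with an instruction to select the actual reason for withdrawal and, for a competing event, to record the event date separately from the date of last contact.
- Reserve the lost-to-follow-up code for patients who meet the protocol's definition.
- Name one instrument, for example Study Stop Point, as the source of both censoring date and reason, and confirm that it has fields for both.
- Reconcile the two withdrawal sections, the Censoring list and the missing-data section, including which instrument sets the inactive status.
- Correct past entries from Study Stop Point, or from chart and SAE records where that form lacks the reason or the date. Entries coded as lost for patients who had completed an assessment within the previous two months are the ones to check first.

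The cost is a small text correction and a modest amount of data cleaning. No clinical rule, sample size or planned analysis changes.
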